9.1.2 Adverse Events

An adverse event is defined as any untoward medical occurrence in a clinical trial subject. The event does not necessarily have a causal relationship with study treatment. The investigator is responsible for ensuring that any adverse events observed by the investigator or reported by the subject are recorded in the subject's medical record.

The definition of adverse events includes worsening of a pre-existing medical condition. Worsening indicates that the pre-existing medical condition or underlying disease (eg, diabetes, migraine headaches, gout) has increased in severity, frequency, and/or duration more than would be expected, and/or has an association with a significantly worse outcome than expected. A pre-existing condition that has not worsened more than anticipated (ie, more than usual fluctuation of disease) during the study or involves an intervention such as elective cosmetic surgery or a medical procedure while on study, is not considered an adverse event.

An adverse device effect is any adverse event related to the use of a medical device. Adverse device effects include adverse events resulting from insufficient or inadequate instructions for use, adverse events resulting from any malfunction of the device, or adverse events resulting from use error or from intentional misuse of the device.

The investigator's clinical judgment is used to determine whether a subject is to be removed from treatment due to an adverse event. In the event a subject, or subject's legally acceptable representative requests to withdraw from protocol-required therapies or the study due to an adverse event, refer to Section 8.1 for additional instructions on the procedures recommended for safe withdrawal from protocol-required therapies or the study.

9.1.3 Serious Adverse Events

A serious adverse event is defined as an adverse event that meets at least 1 of the following serious criteria (unless it meets the definition of a Disease Related Event as defined in Section 9.1.1):

- fatal
- life threatening (places the subject at immediate risk of death)
- requires in-patient hospitalization or prolongation of existing hospitalization
- results in persistent or significant disability/incapacity
- congenital anomaly/birth defect
- other medically important serious event

A disease related event as described above is to be reported as a serious adverse event if:

- the subject's pre-existing condition becomes worse than what the investigator would consider typical for a patient with the same underlying condition, or
- if the investigator believes a causal relationship exists between the investigational medicinal product(s)/protocol-required therapies and the event,
- and the event meets at least 1 of the serious criteria above.

An adverse event would meet the criterion of "requires hospitalization", if the event necessitated an admission to a health care facility (eg, overnight stay).

If an investigator considers an event to be clinically important, but it does not meet any of the serious criteria, the event could be classified as a serious adverse event under the criterion of "other medically important serious event". Examples of such events could include allergic bronchospasm, convulsions, blood dyscrasias, DILI (see Appendix A for drug-induced liver injury reporting criteria), or events that necessitate an emergency room visit, outpatient surgery, or urgent intervention.

9.2 Safety Event Reporting Procedures

9.2.1 Reporting Procedures for Disease Related Events

The investigator is responsible for ensuring that all Disease Related Events observed by the investigator or reported by the subject that occur after the first dose of investigational medicinal product(s)/study treatment/protocol-required therapies through the safety follow-up (ie, 30 days after the last dose of etanercept) are reported using the Event CRF. Additionally, the investigator is required to report a fatal Disease Related Event on the Event CRF.

Events assessed by the investigator to be related to the investigational medicinal product(s)/study treatment/protocol-required therapies, and determined to be serious, require reporting of the event on the Event CRF.

9.2.2 Adverse Events

9.2.2.1 Reporting Procedures for Adverse Events That do not Meet Serious Criteria

The investigator is responsible for ensuring that all adverse events observed by the investigator or reported by the subject that occur after first dose of investigational product through the end of treatment period are reported using the Event CRF.

The investigator must assign the following adverse event attributes:

- Adverse event diagnosis or syndrome(s), if known (if not known, signs or symptoms),
- Dates of onset and resolution (if resolved),
- Severity [and/or toxicity per protocol],
- Assessment of relatedness to etanercept, and
- Action taken

The adverse event grading scale used will be the Common Terminology Criteria for Adverse Events (CTCAE) version 4.0. The grading scale used in this study is described in Appendix A. The investigator must assess whether the adverse event is possibly related to the investigational product. This relationship is indicated by a "yes" or "no" response to the question: Is there a reasonable possibility that the event may have been caused by the investigational product?

If the severity of an adverse event changes from the date of onset to the date of resolution, record as a single event with the worst severity on the Adverse Event Summary CRF.

The investigator is responsible for reviewing laboratory test results and determining whether an abnormal value in an individual study subject represents a clinically significant change from the subject's baseline values. In general, abnormal laboratory findings without clinical significance (based on the investigator's judgment) are not to be recorded as adverse events. However, laboratory value changes that require treatment or adjustment in current therapy are considered adverse events. Where applicable, clinical sequelae (not the laboratory abnormality) are to be recorded as the adverse event.

The Investigator is expected to follow reported adverse events until stabilization or reversibility.

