7.2.4 Safety Follow-up/End of Study

Approximately 30 days (+ 7 days) after their last dose of etanercept, subjects will be contacted by phone by the study staff to follow-up on any continuing serious adverse events or disease related events and inquire about the emergence of any new serious adverse events or disease related events.

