9. SAFETY DATA COLLECTION, RECORDING, AND REPORTING

9.1 Definition of Safety Events

9.1.1 Disease Related Events

Disease Related Events are events (serious or non-serious) anticipated to occur in the study population due to the underlying disease. Disease related events for the purposes of this study include worsening of the skin symptoms associated with PsO. Such events do not meet the definition of an Adverse Event unless assessed to be more severe than expected for the subject's condition.

Disease Related Events and/or Disease Related Outcomes that do not qualify as Serious Adverse Events:

- An event which is part of the normal course of disease under study (eg, disease progression in oncology or hospitalization due to disease progression) is to be reported as a Disease Related Event.
- Death due to the disease under study is to be recorded on the Event CRF.

If the outcome of the underlying disease is worse than that which would normally be expected for the subject, or if the investigator believes there is a causal relationship between the investigational product(s)/study treatment protocol required therapies and disease worsening, this must be reported as an Adverse Event or Serious Adverse Event.

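### After the Week 24/ET visit, non-serious psoriasis worsening judged worse than expected or etanercept-related need not be reported on the CRF, while expected or serious worsening must be, to 30 days after the last dose

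*Protocol*

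**What the plan says.** Protocol 9.1.1 defines worsening of psoriasis skin symptoms as a DRE and adds: "Such events do not meet the definition of an Adverse Event unless assessed to be more severe than expected for the subject's condition". If the outcome is worse than would normally be expected, or the investigator believes the product caused the worsening, "this must be reported as an Adverse Event or Serious Adverse Event".

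The reporting windows then differ by class:

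- **DREs** (9.2.1) run from the first dose "through the safety follow-up (ie, 30 days after the last dose of etanercept) are reported using the Event CRF". The DRE definition in SAP Section 6 gives the same end point.
- **SAEs** (9.2.2.2) run from consent through the 30-day safety follow-up.
- **Non-serious AEs** (9.2.2.1) are those "that occur after first dose of investigational product through the end of treatment period are reported using the Event CRF".

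Table 1 agrees. Its 30-day phone-call column is marked for DREs and SAEs, and its AE row stops at Week 24/ET. Under 7.2.4 the call follows up continuing events of those two classes and is to "inquire about the emergence of any new serious adverse events or disease related events".

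The protocol does not define the end of the treatment period. SAP Section 6 (Study Treatment Period) runs it to the subject's last visit. Its End of Study Date entry identifies that visit as Week 24, or ET for those who leave early.

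**The concern.** The sponsor chose to follow psoriasis worsening for 30 days after the last dose. The reclassification rule in 9.1.1 takes one part of that worsening out of the class being followed and puts it in a class whose window has already closed. The part removed is the part of most interest for safety: non-serious worsening that the investigator finds atypical or attributes to the drug. Worsening that is expected and unrelated stays in.

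The third objective is the safety and tolerability of etanercept in apremilast failures. If the plan is followed exactly, non-serious worsening that begins in late follow-up can reach the study database only if it was judged expected and unrelated. A reader of the report could not tell whether the other kind was absent or merely not collected.

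**Working it through.** The plan states no figure on this point, so there is none to reproduce. The check sets the rules side by side and then counts days.

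**Step 1. Follow each kind of worsening that first appears after Week 24/ET and within 30 days of the last dose.**

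| Worsening | Class | Governing section | CRF report required? |
|---|---|---|---|
| Expected, unrelated, non-serious | DRE | 9.1.1, 9.2.1 | Yes |
| Expected, unrelated, serious | DRE | 9.1.1, 9.1.3, 9.2.1 | Yes |
| Worse than expected or related, serious | SAE | 9.1.3, 9.2.2.2 | Yes |
| Worse than expected or related, non-serious | AE | 9.1.1, 9.2.2.1 | No |

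Three routes are open and one is closed.

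**Step 2. Look for a provision that reopens the fourth route.**

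- 9.2.1 has a sentence on related events, but it covers only those related "and determined to be serious, require reporting of the event on the Event CRF".
- 9.1.2 requires AEs to be entered in the medical record and sets no end date. That is source documentation, not CRF reporting.
- 9.2.2.1 has reported AEs followed to stabilization. This helps a flare reported by Week 24/ET, not a new one.
- The treatment-emergent definition in SAP Section 6 has no end date. It would admit such an event to the tables, but it does not cause the event to be collected.

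None of these requires a CRF entry.

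**Step 3. Size the gap for a completer.** Inputs: one dose per week in the second 12 weeks (Protocol 6.1.1.1); target day = week × 7 + 1 (SAP Appendix A); visit window ±5 days (Protocol 7.2.3); DRE window 30 days after the last dose (Protocol 9.2.1). Assumption: the 12 weekly doses fall on days 85, 92, and so on.

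- Last dose: 85 + 11 × 7 = day 162.
- Week 24 target: 24 × 7 + 1 = day 169.
- End of DRE collection: 162 + 30 = day 192.
- Gap: days 170 to 192, or 192 − 169 = 23 days.
- Week 24 visit 5 days late (day 174): 192 − 174 = 18 days.
- Week 24 visit 5 days early (day 164): 192 − 164 = 28 days.

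**Step 4. Express it as person-time for 80 completers.**

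- 80 × 23 / 365.25 = 5.0 patient-years.
- Range: 80 × 18 / 365.25 = 3.9 to 80 × 28 / 365.25 = 6.1 patient-years.

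After early termination the gap depends on how soon the ET visit follows the last dose, and it approaches 30 days when the two are close. A subject who stops etanercept but keeps attending visits under 8.1 could have a shorter gap or none, if the treatment period is read as lasting to the last visit.

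**The case against.** The strongest reply is that ending non-serious AE collection at Week 24/ET is a deliberate choice, applied consistently in 9.2.2.1, 7.2.4 and Table 1, and that what slips through is narrow. Serious flares are collected to day 30. A clinically important flare that meets no other serious criterion can be classed as another medically important event under 9.1.3. The call asks about psoriasis worsening, so the investigator would probably hear of a flare and record it in the medical record.

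Much of this stands, and it limits the point. It does not close the gap. The upgrade in 9.1.3 is discretionary, and a medical-record entry does not reach the tables. Entering the event as a DRE would contradict 9.1.1. A short AE window may be reasonable for AEs in general, but nothing in the documents explains why the atypical or related part of an event followed for 30 days should be left out.

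Several stronger readings are tempting and are not supported:

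- **Nothing is captured for the whole 30 days, or the call is the only contact after the last dose.** AE collection ends with the treatment period, not at the last dose. The Week 24 visit falls about a week after a completer's last dose and includes PASI, sPGA, BSA, a physical exam and AE collection.
- **Mild flares are kept and severe ones dropped.** The dividing lines are expectedness, relatedness and seriousness. DREs may be serious, and serious unexpected flares are collected.
- **Every flare after stopping etanercept is affected.** The causality test in 9.1.1 concerns the product and the worsening. Return of disease after stopping can be read as normal course, hence a DRE, which is collected.
- **The apremilast rebound figure sizes the problem.** The 4/1184 in Protocol 2.2 concerns another drug and severe worsening, the kind most likely to take the open SAE route. Applied to 80 subjects it gives 80 × 4/1184 = 0.27 events, and it says nothing about non-serious flares on etanercept.
- **The safety results are biased favourably.** Safety is descriptive in a single arm, no table restricted to the post-dose period is planned, and without a flare rate no bias can be sized.

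**Conclusion.** The point holds in a narrow form. Between the Week 24/ET visit and 30 days after the last dose, new non-serious psoriasis worsening that 9.1.1 classes as an AE is the only kind of psoriasis worsening without a required CRF report.

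The 23-day gap (18 to 28) and 5.0 patient-years (3.9 to 6.1) rest on three assumptions: the treatment period ends at Week 24/ET, as the SAP reads it; weekly doses run to day 162; and all 80 subjects complete. These figures measure time without required collection, not events missed. The number of events may be small.

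The documents do not support a claim that the safety conclusions are wrong. They support a claim that one clinically relevant subset could not be reported either way. That is worth correcting because the correction is cheap.

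**What to change.** Reconcile Protocol 9.1.1, 9.2.1, 9.2.2.1, 7.2.4 and Table 1 so that all psoriasis worsening is reported on the Event CRF through 30 days after the last dose, whichever class it falls in:

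- In 9.2.2.1, keep the window open to 30 days after the last dose for non-serious worsening that 9.1.1 moves from DRE to AE, and cross-refer to this from 9.1.1 and 9.2.1.
- In 7.2.4, have the call ask about any worsening of psoriasis, with classification afterwards.
- In Table 1, mark the AE row in the 30-day column, with a footnote limiting it to psoriasis worsening.
- In the SAP safety section, add one table of psoriasis worsening that combines DREs and AEs. The treatment-emergent definition needs no change, since it has no end date.
- Define the end of the treatment period in the protocol.

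Extending collection to all non-serious AEs would also close the gap, but it is optional and does not follow from this defect.

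The cost is protocol wording, one table mark, one SAP table and a few more CRF entries from a call that already takes place. AE incidence may rise slightly. Treatment and visits do not change.

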9.2.2.2 Reporting Procedures for Serious Adverse Events

The investigator is responsible for ensuring that all serious adverse events observed by the investigator or reported by the subject that occur after signing of the informed consent through the 30-day safety follow-up period are recorded in the subject's medical record and are submitted to Amgen. All serious adverse events must be submitted to Amgen within 24 hours following the investigator's knowledge of the event via the Event CRF.

The investigator must assess whether the serious adverse event is possibly related to any study-mandated activity or procedure. This relationship is indicated by a "yes" or "no" response to the question: "Is there a reasonable possibility that the event may have been caused by a study activity/procedure"?

The investigator is expected to follow reported serious adverse events until stabilization or reversibility.

If the electronic data capture (EDC) system is unavailable to the site staff to report the serious adverse event, the information is to be reported to Amgen via an electronic Serious Adverse Event Contingency Report Form within 24 hours of the investigator's knowledge of the event. See Appendix B for a sample of the Serious Adverse Event Worksheet /electronic Serious Adverse Event Contingency Report Form. For EDC studies where the first notification of a Serious Adverse Event is reported to Amgen via the eSerious Adverse Event Contingency Report Form, the data must be entered into the EDC system when the system is again available.

New information relating to a previously reported serious adverse event must be submitted to Amgen. All new information for serious adverse events must be sent to Amgen within 24 hours following knowledge of the new information. The investigator may be asked to provide additional follow-up information, which may include a discharge summary or extracts from the medical record. Information provided about the serious adverse event must be consistent with that recorded on the Event CRF.

If a subject is permanently withdrawn from protocol-required therapies because of a serious adverse event, this information must be submitted to Amgen.

Amgen will report serious adverse events and/or suspected unexpected serious adverse reactions as required to regulatory authorities, investigators/institutions, and IRBs/IECs

in compliance with all reporting requirements according to local regulations and good clinical practice.

The investigator is to notify the appropriate IRB/IEC of serious adverse events occurring at the site and other adverse event reports received from Amgen, in accordance with local procedures and statutes.

9.2.2.3 Reporting Serious Adverse Events After the Protocol-required Reporting Period

There is no requirement to monitor study subjects for serious adverse events following the protocol-required reporting period or after end of study. However, these serious adverse events can be reported to Amgen. In some countries (eg, European Union member states), investigators are required to report serious adverse events that they become aware of after end of study. If serious adverse events are reported, the investigator is to report them to Amgen within 24 hours following the investigator's knowledge of the event.

Serious adverse events reported outside of the protocol-required reporting period will be captured within the safety database as clinical trial cases for the purposes of expedited reporting.

9.2.2.4 Serious Adverse Events That Are not to be Reported In an Expedited Manner

The study population involved will have an increased burden of comorbidities which are commonly associated with psoriasis and may lead to serious adverse events that do not need to be reported in an expedited manner. This includes any serious adverse event attributed to hypertension, obesity, type 2 diabetes, metabolic syndrome, myocardial infarction, angina, coronary artery disease, cerebrovascular accident, peripheral vascular disease, depression and anxiety. These serious adverse events will be monitored with routine pharmacovigilance on an ongoing basis.

9.3 Pregnancy and Lactation Reporting

If a pregnancy occurs in a female subject, or female partner of a male subject, while the subject is taking protocol-required therapies report the pregnancy to Amgen as specified below.

In addition to reporting any pregnancies occurring during the study, investigators should monitor for pregnancies that occur after the last dose of protocol-required therapies through 4-weeks after the end of treatment with etanercept.

The pregnancy should be reported to Amgen's Global Patient Safety within 24 hours of the investigator's knowledge of the event of a pregnancy. Report a pregnancy on the Pregnancy Notification Worksheet (Appendix C).

If a lactation case occurs while the female subject is taking protocol-required therapies report the lactation case to Amgen as specified below.

In addition to reporting a lactation case during the study, investigators should monitor for lactation cases that occur after the last dose of protocol-required therapies through 4 weeks after the end of treatment with etanercept.

Any lactation case should be reported to Amgen's Global Patient Safety within 24 hours of the investigator's knowledge of event. Report a lactation case on the Lactation Notification Worksheet (Appendix C).

10. STATISTICAL CONSIDERATIONS

- 10.1 Study Endpoints, Analysis Sets, and Covariates
- 10.1.1 Study Endpoints

10.1.1.1 Primary Endpoint

• PASI 75 at week 12

10.1.1.2 Secondary Endpoints

- PASI 75 at all other visits
- PASI 50 and 90 at all visits
- Percent PASI improvement at all visits
- sPGA of 0 or 1 at all visits
- sPGA of 0, 1, or 2 at all visits
- sPGA at all visits
- One and two grade improvement in sPGA at all visits
- Percent BSA improvement at all visits
- PSI total and component scores at all visits
- Patient Assessment of Treatment Satisfaction at week 12 and 24
- Improvement in DLQI at week 12 and 24

10.1.1.3 Safety Endpoints

- Adverse events
- Laboratory assessments

10.1.2 Analysis Sets

The full analysis set is all subjects who received at least one dose of investigational product during the study. All safety and efficacy endpoints will be analyzed using the full analysis set.

10.1.3 Covariates and Subgroups

The following predictors and subgroup analyses may be performed to assess their influence on the primary endpoint:

- Body mass index (≤ 35 kg/m² or > 35 kg/m²)
- Body Weight (≤ median, > median)
- Age (<65, ≥ 65)
- Gender (male vs. female)
- Race (white, non-white)
- Ethnicity (Hispanic or Latino, Non-Hispanic or Latino)
- Baseline PASI score (≤ median, > median)
- Baseline BSA with psoriasis involvement (%) (≤ median, > median)
- History of psoriatic arthritis (yes, no)
- Baseline sPGA score (3, 4 or 5)

10.2 Sample Size Considerations

This study will estimate the proportion of subjects with PsO who achieve a PASI 75 after 12 weeks of treatment with etanercept following failure of treatment with apremilast.

In recent etanercept studies, the 12-week PASI 75 response rate for etanercept was ~50 to 60%. The assumed response for a population with failure of treatment with apremilast is 40%. In placebo-controlled phase 3 studies, the PASI 75 placebo response rate was ~5% in subjects with moderate to severe plaque PsO. Therefore, in this single-arm study if the lower bound of the 95% confidence interval for the proportion of PASI 75 response is above 10%, we can safely conclude that in spite of limitations of a single-arm study (ie, regression to the mean and/or placebo effect), the etanercept effect is real.

The sample size of 80 is more than adequate to achieve a half-width of less than 15% for the 95% confidence interval for the proportion of subjects who achieve a PASI 75 response, assuming a sample proportion of 40% and a lower bound of the confidence interval above 10%.

In a phase 3, randomized, double-blind, placebo-controlled apremilast trial, 17% of subjects reported diarrhea and/or nausea. Of the 80 subjects enrolled, 60 subjects will be enrolled for reasons of primary or secondary failure to apremilast in the investigator's opinion. In addition, between 10 and 20 (up to 25%) will be enrolled for reasons of intolerability to apremilast in the investigator's opinion.

